
	
 Taste: NRS (0=terrible to 10=very good). Willingness to reuse the preparation (yes/no).
Study design	
This is a phase II/III, international, multicentre, randomized, parallel-group, endoscopist-blinded study that combines a phase II dose-finding study/pharmacokinetic sub-study with a phase III non-inferiority study.
 
Phase II-dose finding
 
The parallel-group dose-finding phase will involve 150 patients randomly assigned (1:1:1 ratio) to one of the following three treatment groups:
 
• 50 g mannitol powder to be dissolved in 500 ml of water• 100 g mannitol powder to be dissolved in 750 ml of water• 150 g mannitol powder to be dissolved in 1000 ml of water 
Randomization is stratified by centre and by the presence of constipation (yes/no), defined as the recurrent use of laxatives or Bristol Stool Form Scale (BSFS) <3 in the two weeks before randomisation.
 
To limit patient exposure to an ineffective dose causing repetition of colonoscopy, the adequacy of bowel cleansing will be monitored continuously and enrolment in a treatment group will be discontinued as soon as 25% of treated patients present inadequate bowel cleansing causing repetition of colonoscopy. The stopping rule will be applied in each treatment group as follows:
 
• Up to the 25th enrolled patient, enrolment in a treatment group will be stopped as soon as 6 patients present inadequate bowel cleansing causing repetition of colonoscopy.• From the 26th enrolled patient on (if treatment was not discontinued earlier), enrolment will be stopped as soon as 25% of the patients present inadequate bowel cleansing causing repetition of colonoscopy. 
The appropriate mannitol dose to be used in phase III will be singled out based on the following criteria:
 
• 75% or greater rate of adequate bowel cleansing, defined as BBPS total score ≥ 6, with a score for each of the three colon segments (right; transverse, including flexures; and left, including sigmoid and rectum) ≥ 2 during colonoscopy after standard washing and air insufflation for luminal distension.• Rate of patients in safe conditions defined as the absence of potentially dangerous levels of H₂ and CH₄ in each colon segment (right, between ileocecal valve and appendix or as close as possible to the ileocecal valve in case of obstacles that prevent reaching the valve; transverse, including flexures; and left at the sigmoidal-rectum junction, 15-25 cm from anal margin) after standard washing and air insufflation for luminal distension).• Clinical judgment based on the caecal intubation rate, the incidence of adverse events, treatment adherence and acceptability (ease of use, taste and willingness to reuse the preparation). 
Should two or all three doses prove to be equally safe and effective, the lowest dose will be selected for phase III of the study.
 
Phase II-Pharmacokinetic sub-study
 
A single-group design for each mannitol dose will be implemented. Mannitol is contained in foods in a certain amount. To minimize the error of measuring mannitol plasma concentration after the intake of the investigational drug, dietary restrictions are required, after overnight fasting, between 24 hours before and the start of drug self-administration, while fasting is required afterwards up to 8 hours after mannitol intake. Of note, between 4 and 8 hours after mannitol intake, patients may eat any food which complies with the dietary restrictions based on the INRAN tables, if deemed necessary by the Investigator. Venous blood samples will be drawn from a sub-group of at least 10 patients in each dose group at the following times:

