After completion of bowel preparation and prior to colonoscopy, patients will complete the questionnaires on the acceptability of and adherence to the study drug to which they were assigned. The blinded endoscopist will then perform the scheduled colonoscopy using a standard colonoscope recording data on bowel cleansing using the BBPS and measuring intestinal gas (H_2 , CH_4 and O_2) concentrations. The endoscopist will also confirm caecal intubation, defined as identification of the appendiceal orifice. Drugs administered for the procedure will be recorded.

Vital signs (heart rate and blood pressure) will be measured prior to colonoscopy. Oxygen saturation and heart rate will be measured continuously during colonoscopy, but only clinically significant abnormal findings will be recorded on the eCRF, where clinically significant means that these abnormal findings cause an additional control or a medical intervention.

The incidence of adverse events will be recorded.

	
 • Phase II - pharmacokinetic sub-study 
Patients participating in the pharmacokinetic sub-study will sign a separate informed consent form. Venous blood samples will be drawn at the time points mentioned previously and analysed at a centralized bioanalytical laboratory only for the determination of mannitol concentrations.
 
 • Phase III - non-inferiority 
Along with the assessments described for phase II (dose finding), the following additional assessments will be performed:
 
 ○ H_2, CH_4 and O_2 levels will be measured following the introduction of the colonoscope in the sigmoidal-rectum junction (15-25 cm from anal margin) before standard washing and air insufflation. ○ Number, appearance, size location and histological classification of neoplastic and inflammatory colorectal lesions detected. ○ Ottawa Scale for bowel cleansing evaluation before washing and air insufflation for luminal distension. ○ Bowel Cleansing Impact Review (BOCLIR) (at Italian centres only). 
In both phases, the study drugs will not be blinded, but all endoscopists will not be aware of group allocation; patients and site personnel involved in the randomization of the patient and management of the study drugs will be instructed not to disclose group allocation to the endoscopists.

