Mannitol-induced osmotic diuresis and dehydration due to diarrhoea may cause or worsen dehydration/hypovolemia, haemoconcentration and electrolyte imbalances. Administration of mannitol may also cause hyperosmolality. Patients with pre-existing electrolyte disturbances will

be excluded from this study. Furthermore, electrolyte levels and plasma osmolality will be monitored throughout the study.

Laxatives are contraindicated in patients with bowel obstruction, therefore these patients and those with a history of colonic resection will be excluded from this study.

Of note, urine specific gravity may decrease because of osmotic diuresis caused by the well-known pharmacological profile of mannitol. Urine specific gravity out of normal ranges will be collected and managed as expected adverse event.

See the Investigator's Brochure for more details.

Polyethylene glycol + ascorbate (PEG ASC) (Moviprep®)

In the Moviprep® trials, abdominal distension, anal discomfort, thirst, nausea, vomiting, sleep disturbance and abdominal pain were the most common adverse reactions. Dehydration may occur as a result of diarrhoea and/or vomiting. Isolated cases of urticaria, rhinorrhoea, dermatitis, and anaphylactic reaction have been reported with PEG-based products.

Contraindications for the use of Moviprep®

- Hypersensitivity to the active ingredients or other components of Moviprep®
- Intestinal obstruction or perforation
- Gastric emptying disorders
- Ileus
- Phenylketonuria
- Glucose-6-phosphate dehydrogenase deficiency
- Toxic megacolon

Patients with contraindications will not be enrolled in this study.

Precautions for the use of polyethylene glycol + ascorbate (PEG ASC) (Moviprep®)

PEG-ASC should be administered with caution to fragile patients in poor health or patients with serious clinical impairment such as:

- Impaired gag reflex, or with a tendency to aspiration or regurgitation
- Impaired consciousness
- Severe renal insufficiency (creatinine clearance <30 mL/min)
- Cardiac impairment (NYHA grade III or IV)
- Patients at risk of arrhythmia, for example those on treatment for cardiovascular disease or who have thyroid disease
- Dehydration
- Severe acute inflammatory bowel disease

- The medicinal product contains aspartame, which is a source of phenylalanine. This may be harmful for people with phenylketonuria.

See the *simplified Investigational Medicinal Product Dossier (IMPD) for the reference product Moviprep®* for more details.

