4.1.1 PHASE II

The parallel-group dose-finding phase will be conducted at approximately 8 centres and will involve 150 patients randomly assigned (1:1:1 ratio) to one of the following three treatment groups:

- 50 g mannitol powder to be dissolved in 500 ml of water
- 100 g mannitol powder to be dissolved in 750 ml of water
- 150 g mannitol powder to be dissolved in 1000 ml of water

Of note, these doses of mannitol have been selected as this range includes the minimum (50 g) and maximum (150 g) mannitol doses used effectively in the proposed indication, as reported in published literature. Please refer to [Section 2.1](#) for further details.

Randomization is stratified by centre and by the presence of constipation (yes/no), defined as the recurrent use of laxatives or Bristol Stool Form Scale (BSFS) < 3 in the two weeks prior to randomisation.

To limit patient exposure to an ineffective dose causing repetition of colonoscopy, the adequacy of bowel cleansing will be monitored continuously and enrolment in a treatment group will be discontinued as soon as 25% of treated patients present inadequate bowel cleansing causing repetition of colonoscopy. The stopping rule, mainly guided by clinical considerations, will be applied in each treatment group as follows:

- Up to the 25th enrolled patient, enrolment in a treatment group will be stopped as soon as 6 patients present inadequate bowel cleansing causing repetition of colonoscopy (i.e. if among the initial 15 patients enrolled in a treatment group, 6 need to repeat the cleansing procedure, the treatment group will be immediately discontinued).
- From the 26th enrolled patient on (if treatment was not discontinued earlier), enrolment will be stopped as soon as 25% of patients present inadequate bowel cleansing causing repetition of colonoscopy (i.e. if among the initial 32 patients enrolled in a treatment group, 8 need to repeat the cleansing procedure, the treatment group will be immediately discontinued).

The appropriate mannitol dose to be used in the comparative non-inferiority phase (phase III) will be singled out at the end of dose-finding based on the following criteria:

- 75% or greater rate of adequate bowel cleansing.

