8.1.4 LABORATORY TESTS (PHASE II AND PHASE III)

Standard urinalysis, haematological and blood chemistry tests will be performed at Visit 2 (pre-colonoscopy visit) and at Visit 4, 4 hours \pm 30 minutes and 8 hours \pm 30 minutes after the end of study drug self-administration. A blood beta hCG pregnancy test is required for women of childbearing potential at Visit 2. The lab tests to be performed are listed in the Table below and are to be performed in both phase II and phase III.

Laboratory Assessments		
Haematology	Serum chemistry	Urine analysis

• Haematocrit (Hct)• Haemoglobin (Hb)• Mean corpuscular haemoglobin (MCH)• Mean corpuscular haemoglobin concentration (MCHC)• Mean corpuscular volume (MCV)• Platelet count• Red blood cell (RBC) count• White blood cell (WBC) count with differential	
• Alanine aminotransferase (ALT)• Aspartate aminotransferase (AST)• Total bilirubin• Direct bilirubin• Blood Urea Nitrogen (BUN)• Creatinine• eGFR estimated by means of simplified MDRD equation• Potassium• Sodium• Phosphorus• Calcium• Chloride• Glucose• Pregnancy test (beta hCG at Visit 2)	
• Appearance• pH• Protein• Glucose• Ketone bodies• Indicators of blood and WBCs• Specific gravity*• Urobilinogen

*Urine specific gravity may decrease because of osmotic diuresis caused by mannitol. The event is to be considered expected.

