8.2 SAFETY

The assessment of overall safety consists in recording and evaluating all adverse events, haematological and chemical parameters (see [Section 8.1.4](#)), and vital signs. The following adverse events are of particular interest in this study:

- Nausea, vomiting, abdominal pain, bloating, thirst, dizziness, sleep disturbance, hypotension
- Acute disruption of electrolyte homeostasis
- Complications of colonoscopy: colonic perforation, bleeding, cardiovascular complications, explosion

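### Section 2.2.1 promises plasma osmolality monitoring for a named mannitol risk, but the Section 8.1.4 test list omits it and no other section assigns it

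*Combined protocol and SAP*

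**What the plan says.** Section 2.2.1 (Known Potential Risks), under the mannitol heading, discusses osmotic diuresis, dehydration and electrolyte imbalance, and then states: "Administration of mannitol may also cause hyperosmolality". After noting that patients with electrolyte disturbances are excluded, the same paragraph ends: "Furthermore, electrolyte levels and plasma osmolality will be monitored throughout the study". It gives no method, time points, threshold or action for osmolality.

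Section 8.1.4 (Laboratory Tests) sets the timing: "Standard urinalysis, haematological and blood chemistry tests will be performed at Visit 2 (pre-colonoscopy visit) and at Visit 4", with the Visit 4 samples taken 4 and 8 hours after the end of self-administration. It then fixes the content: "The lab tests to be performed are listed in the Table below and are to be performed in both phase II and phase III". Sections 8.1.1, 8.1.2 and 8.1.3 all send the reader to 8.1.4 for the laboratory details.

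**The concern.** Section 2.2.1 is where an ethics committee or authority reads which risks have been recognised and how they are controlled. Section 2.2.3 builds its very-low-risk conclusion on what precedes it. If a safeguard stated there is missing from the operative test list, reviewers have been told of monitoring that a site following the list would not carry out.

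The risk is not remote from the population studied. Section 2.2.1 itself links insufficient renal excretion to mannitol accumulation. Section 5.2 excludes only an eGFR below 30 ml/min/1.73 m², so patients with lesser renal impairment can enter, and phase II doses reach 150 g.

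What is at stake is safety monitoring. No efficacy endpoint or dose-selection criterion uses osmolality.

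**Working it through.** The plan gives no figure to reproduce. The check sets the commitment against every place where it could be carried out.

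**1. The Section 8.1.4 table, counted by column**

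| Column | Entries | Content relevant here |
|---|---|---|
| Haematology | 8 | haematocrit |
| Serum chemistry | 14 | potassium, sodium, phosphorus, calcium, chloride; also BUN, creatinine, eGFR, glucose |
| Urine | 8 | specific gravity |
| Total | 8 + 14 + 8 = 30 | electrolytes 5, osmolality 0 |

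The electrolyte half of the Section 2.2.1 commitment is carried out and the osmolality half is not. The table shows no redaction or gap that could hide an entry.

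**2. Other places that could assign the test**

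- Schedules of activities (1.2.1 and 1.2.2): one generic row for haematology, chemistry and electrolytes. They name no individual chemistry test, so their silence proves nothing; 8.1.4 supplies the detail.
- Endpoint lists (synopsis and Section 3): the parentheses after the laboratory endpoint omit bilirubin, which is in the 8.1.4 table. They are not complete lists, so I do not rely on their silence.
- Section 8.2: refers back to 8.1.4 for the laboratory parameters. Its events of particular interest include "Acute disruption of electrolyte homeostasis" but not hyperosmolality.
- Section 9.4.2: summarises chemical parameters generically, without naming osmolality.
- Pharmacokinetic sub-study: its samples are "analysed at a centralized bioanalytical laboratory only for the determination of mannitol concentrations". They also cover few patients and only phase II: "Venous blood samples will be drawn from a sub-group of at least 10 patients in each dose group".
- Section 2.1: refers to osmolarity in the gut as the mechanism of action, which is not a plasma measurement.

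Plasma osmolality as a measurement therefore appears once, in Section 2.2.1, and nowhere operative.

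**3. Planned patients covered by the table**

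- Mannitol: 3 × 50 + 348 = 498 (Section 9.1).
- Both arms: 150 + 696 = 846.

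These are planned counts. A phase II arm can close early, since "enrolment in a treatment group will be discontinued as soon as 25% of treated patients present inadequate bowel cleansing causing repetition of colonoscopy", and Section 9.1 allows the phase III sample size to be re-estimated.

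**4. Assays needed if the test is added at the three existing draws**

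- All patients: 3 × 846 = 2,538.
- Mannitol patients: 3 × 498 = 1,494.
- Moviprep patients: 3 × 348 = 1,044, which is 1,044 / 2,538 = 41% of the total.

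**The case against.** The mismatch itself is hard to dispute. The case on the other side concerns how to read it and how much it matters.

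*Monitoring need not mean a direct assay.* Sodium, glucose and BUN are in the table, so an osmolality could be calculated from them. However, the protocol states no calculation, formula or derived variable, and a value built from those three analytes would leave out mannitol, the solute of concern. This reading does not resolve the contradiction.

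*The sentence in 2.2.1 may be the error.* It is background narrative without time points or thresholds, and Amendment 4 corrected the 8.1.4 table without adding osmolality. The text alone cannot show which section reflects the sponsor's intent. Against that, Amendment 2 handled urine specific gravity in 2.2.1 and 8.1.4 together, so the two sections have been treated as linked. Deleting the sentence would also withdraw a safeguard stated for a named risk, which would need its own justification.

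*Testing the Moviprep arm goes beyond a mannitol risk.* This is true of 41% of the assays. But the table already applies to both arms, and comparator values help in interpreting those in the mannitol arm.

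*Indirect protection is substantial.* This stands:

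- Electrolytes, BUN, creatinine, eGFR, glucose, haematocrit and urine specific gravity are measured at 4 and 8 hours.
- Thirst, dizziness and hypotension are events of particular interest.
- Electrolyte disturbance, an eGFR below 30 and NYHA class III–IV are exclusions.
- About one litre of liquid follows the mannitol dose.
- Mannitol is only partly absorbed and is taken once.
- The adverse events listed in Section 2.2.1 for 433 earlier mannitol patients do not include hyperosmolality.

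These points limit the weight of the finding. They do not supply the measurement that was promised.

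**Conclusion.** The concern holds. Section 2.2.1 commits to monitoring plasma osmolality, Section 8.1.4 lists 30 tests without it, and no other section assigns it. The gap covers 498 planned mannitol patients; that figure is a headcount, and no harm rate is claimed.

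This should be corrected as a safety-monitoring inconsistency. It does not touch the non-inferiority analysis, the sample size or the type I error.

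Confidence is high for the textual contradiction, which rests on the document's own words. It does not extend to what sites did: the Investigator's Brochure and Study Manual are not available, and either could have arranged the test.

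**What to change.** Add measured plasma osmolality to the serum chemistry column of the Section 8.1.4 table, at Visit 2 and at 4 and 8 hours after the end of self-administration. Section 2.2.1 gives no time points; these three are proposed because blood is already drawn then, and Visit 2 serves as the baseline. The schedules of activities and the chemical-parameter summary in Section 9.4.2 are worded generically, so they would take in the new test without change.

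The cost is one more assay per existing draw: three per patient, or 2,538 at the planned 846, with no additional visit or venepuncture. Tube type, sample volume and local laboratory capability are not stated and need checking first. An amendment helps only patients not yet treated.

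If the sponsor considers osmolality unnecessary, Section 2.2.1 must be corrected and the reason given. The two sections should not be left as they stand.

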2.2.2 KNOWN POTENTIAL BENEFITS

The ideal method of bowel preparation for colonoscopy is a combination of effectiveness, safety, ease of self-administration, good patient acceptance and low cost. While current available preparations offer effectiveness and safety at a reasonable level, patient acceptance can still be improved. A bowel cleansing agent such as mannitol, which has a much better flavour than other cleansing agents, requires low volume and is self-administered the morning of the procedure (and thus does not interfere with sleep), is expected to improve patient compliance and thus the success of the procedure.

2.2.3 ASSESSMENT OF POTENTIAL RISKS AND BENEFITS

In light of what outlined previously, the risk connected with this study is considered to be very low and is minimized by the use of a gas detector that will help performing electrocautery, if necessary, in safe conditions. Further information about the gas detector is available in the *Gas Detector Technical Documentation*. The expectation is to show that mannitol is not inferior to 2L PEG ASC in terms of bowel cleansing, while better in terms of patient acceptance. The development of oral mannitol for bowel cleansing and the conduct of this study are therefore justified.

3 OBJECTIVES AND ENDPOINTS

Phase II - Dose Finding/Pharmacokinetic sub-study	
Objectives	Endpoints
To determine the effective and safe dose of mannitol for adequate bowel cleansing to be used in the comparative non-inferiority phase of the study (phase III).	
Primary efficacy endpoint
 
Proportion of patients with adequate bowel cleansing, defined as Boston Bowel Preparation Scale (BBPS) total score ≥ 6, with a score for each of the three colon segments (right; transverse, including flexures; and left, including sigmoid and rectum) ≥ 2 during colonoscopy after standard washing and air insufflation for luminal distension. 
Secondary efficacy endpoint
 
Caecal intubation rate, defined as the percentage of patients with appendiceal orifice visible to the endoscopist. 
Safety and tolerability
 
Proportion of patients in safe conditions, defined as the absence in each colon segment (right, between ileocecal valve and appendix or as close as possible to the ileocecal valve in case of obstacles that prevent reaching the valve; transverse, including flexures; and left at the sigmoidal-rectum junction, 15-25 cm from anal margin) of potentially dangerous levels of H_2 and/or CH_4 ($>4\%$ Vol and $>100\%$ of Lower Explosion Level (LEL), respectively) during colonoscopy after standard washing and air insufflation for luminal distension.Incidence of adverse events from the beginning of study drug self-administration.Proportion of patients with change from baseline considered clinically significant by the Investigator of haematological and chemical parameters (CBC, creatinine, BUN, eGFR, ALT, AST, glucose, electrolytes) 4 hours and 8 hours after completion of study drug self-administration, where clinically significant means that the change causes an additional control or a medical intervention.Proportion of patients with change during colonoscopy considered clinically significant by the Investigator of vital signs (heart rate and pulse oximetry), where clinically significant means that the change causes an additional control or a medical intervention.

Phase II - Dose Finding/Pharmacokinetic sub-study	
Objectives	Endpoints
To define the pharmacokinetic profile of the mannitol doses used in dose finding through a pharmacokinetic sub-study.	
Adherence and acceptability
 
 • Adherence: study drug completely taken, partially taken, not taken • Ease of use: numeric rating scale (NRS) (0 = very difficult to 10 = very easy) • Taste: NRS (0 = terrible to 10 = very good) • Willingness to reuse the preparation (yes/no) 
• C_{max}: maximum concentration
 
• t_{max}: time to maximum concentration
 
• $AUC_{0-t_{0-}}$: area under concentration-time curve, from 0 to the last blood sampling time point with measurable concentration
 
• $t_{1/2}$: elimination half-life

Phase III - Non-Inferiority	
Objectives	Endpoints
To demonstrate the non-inferiority of mannitol vs. standard split 2L PEG ASC (Moviprep®) in bowel cleansing for colonoscopy.	
Primary Efficacy endpoint
 
 • Proportion of patients with adequate bowel cleansing, defined as BBPS total score ≥ 6, with a score for each of the three colon segments (right; transverse, including flexures; and left, including sigmoid and rectum) ≥ 2 during colonoscopy after standard washing and air insufflation for luminal distension. 
Secondary efficacy endpoints
 
 • Number, appearance, size, location and histological classification of neoplastic and inflammatory colorectal lesions detected. • Adenoma detection rate, defined as the percentage of patients with at least one lesion detected. • Caecal intubation rate, defined as the percentage of patients with appendiceal orifice visible to the endoscopist. • Ottawa Scale for bowel preparation before washing and air insufflation for luminal distension.
To assess the safety and tolerability of mannitol.	
 • Proportion of patients in safe conditions, defined as the absence in each colon segment (right, between ileocecal valve and appendix or as close as possible to the ileocecal valve in case of obstacles that

[figure not shown]
Phase III - Non-Inferiority	
Objectives	Endpoints
	
prevent reaching the valve; transverse, including flexures; and left at the sigmoidal-rectum junction, 15-25 cm from anal margin) of potentially dangerous levels of H₂ and/or CH₄ (>4% Vol and >100% LEL, respectively) during colonoscopy after standard washing and air insufflation for luminal distension.
 
• Incidence of adverse events from the beginning of study drug self-administration.• Proportion of patients with change from baseline considered clinically significant by the Investigator of haematological and chemical parameters (CBC, creatinine, BUN, eGFR, ALT, AST, glucose, electrolytes) 4 hours and 8 hours after completion of study drug self-administration, where clinically significant means that the change causes an additional control or a medical intervention.• Proportion of patients with change from baseline considered clinically significant by the Investigator of vital signs (heart rate, systolic and diastolic blood pressure) measured during visits, as well as clinically significant change of pulse oximetry and heart rate measured during colonoscopy and systolic and diastolic blood pressure measured immediately prior and after colonoscopy, where clinically significant means that the change causes an additional control or a medical intervention. Of note, clinically significant changes of systolic and diastolic blood pressure measured during colonoscopy will also be reported if considered clinically significant by the Investigator.
To evaluate adherence to and acceptability of bowel preparation with mannitol and with Moviprep®.	
• Adherence: study drug completely taken, partially taken, not taken• Bowel Cleansing Impact Review (BOCLIR) (only at Italian centres)• Ease of use: NRS (0 = very difficult to 10 = very easy)• Taste: NRS (0 = terrible to 10 = very good)• Willingness to reuse the preparation (yes/no)

